Our primary endpoints will be postoperative pain as measured by total postoperative morphine or hydromorphone utilization from a patient controlled anesthesia pump (PCA) and pain scores on visual analog scale (VAS). The VAS will be measured while the patient is at rest (VAS-R) and after the patient is asked to cough (VAS-C). For each patient, the area under the curve (AUC) of the VAS-R will be calculated. Morphine usage will be tracked by patient controlled analgesia (PCA) dispensed. Using the medication chart, any rescue medications beyond the PCA will also be recorded. Patients will be interviewed and asked to rate their postoperative pain on a 10-point scale with 0 being no pain and 10 being the most pain. Another variables recorded will include incidents of nausea or vomiting, time to first ambulation, and time to first liquid and solid oral intake. All measurements for variables were obtained at 6 hrs, 12 hrs, 24 hrs, 48 hrs, 72 hrs. Nursing staff on our designated breast reconstruction floor will be instructed on how to interview patients and collect data for the 6 and 12 hour timepoints. This information will be stored on Epic EMR in a stardard note and nurses will be given a smart text to use in order to appropriately ascertain all information. The 24, 48, and 72 hour time points will be collected by the co-investigators. Any pain medications given by PCA, IV or PO will recorded and converted to morphine as diagramed below:

Drug	Parenteral (mg)	Oral (mg)
Morphine	10	30
Hydromorphone	1.5	7.5
Oxycodone	NA	20
Hydrocodone	NA	30-45
Oxymorphone	1	10
Meperidine	75	300
Codeine	130	200

Equianalgesic Potency Conversion TABLE A

Discuss limitations and difficulties

The limitations of our study include potential confounding pain from the mastectomy site, the subjectivity in patient perception of pain, and differences in patient threshold to request patient- controlled anesthesia and oral narcotics

Provide the tentative schedule for completion

Our schedule for the study will be 6 months continuous enrollment and experimentation from September to February, or until our groups are filled.

Data collection

The data fields will be: Birth date, sex, type of surgery, utilization of mesh, number of mg on PCA, VAS at rest and VAS with cough, number of rescue pain medications given, number of incidents of nausea/vomiting, time to first ambulation, time to first liquid and solid intake post surgery.

Planned Data Analysis

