The data will be examined with an analysis of variance (ANOVA) procedure with repeated measures. The design will have one between factor, (group (3), and one within factor, time (6). The analysis will test for a group effect, a time effect and a group by time interaction. We anticipate that the three groups will be comparable at the start. This implies the likelihood of a significant interaction term. If this happens, our primary analysis will focus on the ANOVA for the 72-hour time point. This will show us if a differential effect has occurred. All assumptions of the test will be examined and data transformations or nonparametric methods used if indicated.

We will not be utilizing QHS, rather, one of the plastic surgery residents, [name], will serve as our statistician.

Sample Size Justification

We propose to randomly assign individuals recruited during the recruitment period into 3 equal groups. With three groups this translates to a difference between groups of 5 for total morphine used on day 3 and 0.7 for the VAS. This assumes standard deviations of 4.9 for morphine and 0.7 for VAS. Effects of these sizes represent clinically important differences in the range that we believe will happen.

References:

- Feng LJ. Painless abdominoplasty: the efficacy of combined intercostal and pararectus blocks in reducing postoperative pain and recovery time. Plast Reconstr Surg. 2010 Nov;126(5):1723-32.

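### The declared primary endpoint is total postoperative PCA opioid, but a significant interaction test moves the primary analysis to the 72-hour value, and no primary contrast is named otherwise

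*Combined protocol and SAP*

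**What the plan says.** **Endpoint (Post-operative Protocol).** "Our primary endpoints will be postoperative pain as measured by total postoperative morphine or hydromorphone utilization from a patient controlled anesthesia pump (PCA"), together with VAS pain scores at rest and with cough. An AUC of VAS at rest is to be calculated for each patient. On timing: "All measurements for variables were obtained at 6 hrs, 12 hrs, 24 hrs, 48 hrs, 72 hrs".

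**Analysis (Planned Data Analysis).** A repeated-measures ANOVA with three groups and "one within factor, time (6") tests group, time and their interaction. The text starts from an expectation about the arms: "We anticipate that the three groups will be comparable at the start". From that it draws an inference about the interaction test: "This implies the likelihood of a significant interaction term". It then sets out what follows for the primary analysis: "If this happens, our primary analysis will focus on the ANOVA for the 72-hour time point". It does not say which test is primary if the interaction is not significant, and it does not mention the VAS AUC.

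**Sample size (Sample Size Justification).** The planning difference is "a difference between groups of 5 for total morphine used on day 3 and 0.7 for the VAS". On variability, the section adds: "This assumes standard deviations of 4.9 for morphine and 0.7 for VAS". No sample size, power or alpha is given.

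**The concern.** Two different opioid quantities carry the word primary: the postoperative total in the endpoint text, and the 72-hour value in the analysis text. The day-3 wording under Sample Size Justification fits the second. Nothing reconciles them, and the choice is left to a test on the trial's own outcome data.

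The plan does not say whether an opioid value recorded at 72 h is the amount since the previous reading or a running total. If it is an interval amount, the 72-hour ANOVA does not test the declared total. An arm that truly lowers total use could then be reported as showing no primary difference, or the reverse.

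VAS has the same problem. The switch bypasses the AUC that the endpoint text plans to calculate.

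The reason given for expecting an interaction is also weak on the listed schedule. Groups are expected to be comparable at the start, but the first listed reading is at 6 h, after treatment has been given.

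**Working it through.** **1. Plan's own figure.** There is none to reproduce, because sample size, power and alpha are not stated.

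**2. Are the pilot readings running totals?** On-Q, 6 to 72 h (Significance section): 16.42, 14.8, 14.9, 11.63, 12.65 mg. Exparel: 6.2, 5.5, 5.98, 5.23, 2.7 mg. A running total cannot fall, so these are not running totals.

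**3. How far apart are the two quantities?** Treat the pilot readings as non-overlapping interval amounts (an assumption) and omit the 30-minute reading, which the new schedule does not list.
- Exparel: 6.2 + 5.5 + 5.98 + 5.23 + 2.7 = 25.61 mg
- On-Q: 16.42 + 14.8 + 14.9 + 11.63 + 12.65 = 70.40 mg
- Difference in sums: 70.40 − 25.61 = 44.79 mg
- Difference at 72 h: 12.65 − 2.7 = 9.95 mg; 9.95 / 44.79 = 22%

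**4. Which branch tests the total?** Assume that the unstated fallback is the group main effect.
- Interval amounts: the main effect tests the sum of the readings, hence the total; the 72-hour ANOVA does not.
- Running totals: the 72-hour ANOVA tests the total; the main effect weights the five intervals 5, 4, 3, 2, 1 over 15, that is 33, 27, 20, 13 and 7%.

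On either definition only one branch tests the declared endpoint.

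**5. Operating characteristics (simulation).** Assumptions: alpha 0.05; five readings; SD 4.9 mg at each; compound-symmetry correlation 0.3 to 0.7; one arm differs; uncorrected interaction F test; main effect as fallback. Arm size is assumed:
- 16 per arm: 2 × (1.96 + 0.84)² × (4.9/5)² = 15.1, which is 16 after the t correction (80% pairwise power).
- 10 per arm: the middle of 54/2/3 = 9 and 66/2/3 = 11, if every patient at the 2014 and 2013 volumes enrols for six months.

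Ranges run from correlation 0.3 to 0.7.

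| True difference at 6, 12, 24, 48, 72 h (mg) | Per arm | Rule as written | Test of total |
|---|---|---|---|
| Fading: 5, 3.75, 2.5, 1.25, 0 | 16 | 29-7% | 58-36% |
| Growing: 0, 1.25, 2.5, 3.75, 5 | 16 | about 76-81% | 58-36% |
| Constant 5 | 16 | 98-92% | 99.5-92% |
| Pilot: 10.22, 9.30, 8.92, 6.40, 9.95 | 16 | about 100% | about 100% |
| Fading | 10 | 27-10% | 37-23% |
| Growing | 10 | 49-54% | 37-23% |

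A crossing profile shows the mismatch directly. With shifts of +2, +1, +1, +1 and −5 mg the totals are equal (sum 0). At 16 per arm and correlation 0.5, the test of the total rejects in 5% of trials and the rule in 83%.

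Sensitivity: if SD and effect instead scale with interval length (6, 6, 12, 24, 24 h, keeping 4.9 for the last), the fading loss at 16 per arm almost vanishes (rule 23-15%, total 24-16%).

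**6. How often does the switch fire?** With the pilot differences and five readings: 34-73% of trials at 16 per arm and 20-47% at 10. The analysis text has six times, and the pilot's sixth was 30 minutes, where the difference ran the other way (1.2 − 5.2 = −4.0 mg). With that reading added, the switch fires in about 100% of trials at both sizes.

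**7. Type I error of the rule.** 5.1-5.6% under compound symmetry and 5.5-6.3% under AR(1) correlation, over the cases run (10 to 30 per arm).

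**The case against.** The strongest defence is that the rule is written in advance, that looking by time after an interaction is conventional, and that the analysis and sample-size text agree with each other on day 3. Most of that is fair. This is not an unplanned change. The day-3 wording is not a third quantity either: it most naturally means use from 48 to 72 h, which is what a 72-hour interval reading would measure. But agreement between those two sections leaves both in conflict with the declared total, and stating a switch in advance does not make its two branches answer the same question.

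A second defence is that the 72-hour value may be cumulative. The plan does not exclude this, but the pilot readings and the day-3 wording both point to interval amounts. If the values were cumulative, the assumed fallback would be the branch that misses the total.

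A reader might infer four stronger things that the documents do not support:
- **Inflated false positives.** The rule's error rate is about 5-6%.
- **A general loss of power.** The rule loses for fading effects, gains for growing ones, and both tests reach about 100% with the pilot differences, the only opioid effect shape that the documents supply.
- **That chance alone picks the question.** That depends on counting five readings. With the 30-minute reading as the sixth, the 72-hour value becomes primary almost always, and what remains is the mismatch with the declared endpoint.
- **That the VAS AUC would recover the early pilot VAS difference.** It would not. Over 6-72 h the 6-hour reading has weight (6/2)/66 = 4.5%. For a difference at 6 h only, the AUC has 5% power, against 8-5% for the rule (16 per arm; difference and SD both 0.7).

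**Conclusion.** The point holds. The documents contain two primary opioid quantities, a preliminary test on the final data decides whether the 72-hour one is used, and the other branch has no named primary contrast. This follows from the text and needs no simulation.

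The size of the gap is illustrated by the pilot: the 72-hour difference is 22% of the summed difference, if readings are non-overlapping interval amounts. The power figures rest on assumed arm sizes, correlations, effect shapes, equal SDs and a main-effect fallback that the plan does not state. They show that the two tests can disagree in either direction, not that one is uniformly better. The consequence is a primary result that may not answer whether total opioid use was lower. It should be settled before outcome data are examined, because a choice made afterwards would not be credible.

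**What to change.** **Change.**
- Delete the interaction-triggered switch from Planned Data Analysis.
- Name one opioid primary quantity, test it across the three groups whatever the interaction shows, and use it in the endpoint, analysis and sample-size text. The default that follows the endpoint text is each patient's total PCA opioid through 72 h in morphine equivalents. If the sponsor means day 3, make that primary unconditionally and change the endpoint text to match.
- State whether recorded opioid values are interval amounts or running totals.
- Restate the planning difference and SD for the chosen quantity.
- For VAS, use one unconditional summary. The AUC of VAS at rest, already planned, is the natural choice. State that VAS with cough is secondary, or give it its own summary.
- Keep the repeated-measures model and by-time estimates, including 72 h, as supportive. Reconcile the six time levels in the analysis with the five listed times.

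**Cost.** A few sentences. Milligrams on PCA are already a data field. Conversion also needs the drug in the pump, and Specific Aims already calls for the type of narcotic.

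The SD of 4.9 cannot be carried over to a total. If it applied at each of five readings, the SD of the sum would be 4.9 × √(5 + 20 × correlation), or 16.3 to 21.4 mg for correlation 0.3 to 0.7. At 16 per arm and 80% pairwise power (detectable difference 1.0237 SD), that corresponds to 16.6 to 21.9 mg.

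**Downsides.** The total has less power than the present rule if the effect is late or growing (58-36% against about 76-81% at 16 per arm). The AUC of VAS at rest will not detect a difference confined to 6 h. VAS with cough loses its place in the primary test unless it is given its own summary.
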